10.7.2.5 Nasal Discharge Endpoints

Total Weight of Mucus Produced Starting at Initial Administration of IMP up to Planned Discharge from Quarantine

Total weight of nasal mucus (grams) will be calculated as the sum of mucus weights taken from the assessment at the time of the first administration of IMP (can be prior to or after dosing, depending on whether dosed in the morning or evening) to morning of Day 12 (Quarantine discharge). Total mucus weight will be summarised by treatment group and will include the change from baseline, where baseline is the last assessment recorded prior to receiving a positive result for RSV by qicPCR. For participants who did not receive a positive result, the final assessment prior to the first administration of IMP will be defined as the baseline score.

Total Number of Tissues Used by Participants Starting At Initial Administration of IMP up to Planned Discharge from Quarantine

Total number of tissues will be counted from the assessment at the time of the first dose of IMP (can be prior to or after dosing, depending on whether dosed in the morning or evening) to morning of Day 12 (Quarantine discharge). This count will be summarised by treatment group and will include the change from baseline, where baseline is the last assessment recorded prior to receiving a positive result for RSV by qicPCR. For participants who did not receive a positive result, the final assessment prior to the first administration of IMP will be defined as the baseline score.

CCI

[REDACTED]

[REDACTED]

[REDACTED]

[REDACTED]

CCI

CCI

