8.3.3. Nasal Discharge Collection from Paper Tissues

Each participant will be given pre-weighed packets of paper tissues. Participants will be asked to place single tissues used for nose blowing or sneezing into a specified collection bag (for that participant only).

A daily 24-hour paper tissue collection will take place throughout the quarantine period. Distribution of paper tissues and collection bags will start on Day -1, with the first collection on Day 0. Thereafter, collection of paper tissues will occur at the same time each day (± 1 hour) with tissues distributed 24 hours ahead.

24-hour paper tissue collections will be analysed to determine the following over the quarantine period:

- 24-hour nasal discharge weight
- The number of paper tissues used for nose blowing or sneezing over each 24-hour period

CCI [REDACTED]

[REDACTED]

[REDACTED]

[REDACTED]

[REDACTED]

[REDACTED]

[REDACTED]

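### The change from baseline for total mucus weight and tissue count sets a multi-day sum against one 24-hour collection, so it cannot be read as a change

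*SAP*

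**What the plan says.** The unit of measurement is a day. Protocol 8.3.3 states: "A daily 24-hour paper tissue collection will take place throughout the quarantine period". Each collection yields a discharge weight and a tissue count for that period.

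SAP 10.7.2.5 adds these up to the morning of Day 12. For mucus: "Total weight of nasal mucus (grams) will be calculated as the sum of mucus weights", starting at the assessment at first administration. For tissues: "Total number of tissues will be counted from the assessment at the time of the first dose of IMP". In both cases the SAP allows that opening assessment to fall before or after dosing.

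Both totals are then given a change from baseline. For mucus: "Total mucus weight will be summarised by treatment group and will include the change from baseline, where baseline is the last assessment recorded" before a stated point. For tissues: "This count will be summarised by treatment group and will include the change from baseline". For participants with a positive qicPCR, "baseline is the last assessment recorded prior to receiving a positive result for RSV by qicPCR". For the others, "the final assessment prior to the first administration of IMP will be defined as the baseline score". Either way the baseline is one collection. Nothing in the section scales it to the length of the window or divides the total by the number of collections.

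The planned outputs do not match the text:

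- **Table list.** SAP 13.2 titles Tables 14.2.4.1 and 14.2.4.2 as results by assessment.
- **Shell.** SAP Section 14 gives both the layout of Table 14.2.3.7.1, a single block of statistics with no daily rows and no change column. There the mucus title has lost its by-assessment ending and the tissue title keeps it.
- **Listing.** Listing 16.2.6.4.1 shows each total once, against Day 12, with no baseline or change.

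Protocol Section 3 names only the totals as endpoints, and Protocol Table 9-2 assigns them no inferential analysis. The change from baseline is a SAP addition that SAP Section 11 does not record.

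**The concern.** A change from baseline should be zero for a participant whose discharge stays at its baseline level throughout. A multi-day sum minus one day's value is not zero for that participant. It is nearly the whole sum. It also grows with the number of days summed, and that number is set by when dosing began.

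What is at stake is a number in the report for two secondary endpoints that carries the name of a change but is almost the total again. It does little of what a baseline correction is for, which is to remove differences between participants in their usual discharge.

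**Working it through.** **Inputs.** The dosing start is the evening of Day 2 at the earliest and the evening of Day 5 at the latest (SAP 6.1). The window ends on the morning of Day 12, and one assessment is one 24-hour collection. Count am as .0 and pm as .5 of a day.

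**Reproducing the plan's own figure.** The first sensitivity analysis in SAP 10.7.1.2 gives 6.5 days and 14 nasal washes for a Day 5 evening start. Here 12.0 − 5.5 = 6.5 days, and 1 + 6 × 2 + 1 = 14 washes. Both agree. The same dosing and discharge times bound the nasal discharge totals. The documents give no figure for the discharge change itself.

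**Baseline left in the change.** Let k be the number of collections in the sum T, B the baseline collection and b a stable usual level per day. T contains k × b. The stated change, T − B, still contains (k − 1) × b, a share of (k − 1)/k.

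| First dose | Elapsed days | k, days after the dosing day | Share left | k with the dosing-day collection | Share left |
|---|---|---|---|---|---|
| Day 2 pm | 12 − 2.5 = 9.5 | 12 − 2 = 10 | 9/10 = 90% | 11 | 10/11 = 91% |
| Day 5 pm | 12 − 5.5 = 6.5 | 12 − 5 = 7 | 6/7 = 86% | 8 | 7/8 = 88% |

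The share of between-participant variance in usual level that stays is the square: (6/7)² = 73% for k = 7 and (9/10)² = 81% for k = 10.

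**A participant who never departs from baseline.** T − B is 6b for k = 7 and 9b for k = 10. The like-for-like versions, T − kB and T/k − B, are both 0. The documents give no mucus weights, so any value of b is an assumption. For b from 0.5 to 5 g/day, the apparent change is 3 to 30 g (k = 7) or 4.5 to 45 g (k = 10).

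**Dependence on dosing start.** Assume b = 1 and a constant excess of 2 per day.

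| k | T | T − B | T − kB | T/k − B |
|---|---|---|---|---|
| 7 | 21 | 20 | 14 | 2 |
| 10 | 30 | 29 | 20 | 2 |

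The daily process is the same, yet T − B differs by 9. T − kB removes the baseline but still accumulates over a longer window. Only the daily form is equal in both rows.

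**Illustrative simulation.** The assumed SDs are 1 for usual level, 0.25 to 1.0 for daily noise, and 1 per day for the illness effect. Correlation with the true usual level is 0.68 to 0.71 for T, 0.62 to 0.67 for T − B, and 0.00 for T − kB. The SD of T − B is 93% to 96% of the SD of T.

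**Comparison within the SAP.** For the change-from-baseline symptom AUC, SAP 10.7.2.4 takes the change at each assessment and then accumulates it. That removes the baseline over the whole window. Nasal discharge has no such step.

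**Overlap.** For a never-positive participant, the baseline is the last collection before first IMP, and the sum may open with a collection made before dosing. These can be the same collection. T − B then only deletes the first term of T.

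**The case against.** The SAP never writes out total minus baseline. The by-assessment titles in SAP 13.2 fit a daily change, which would be valid, and the shell has no change column, so the faulty number may never be printed. This is fair as far as intent goes. It does not settle the rule: the text attaches the change to the total, and the title, shell and listing disagree with it and with one another. A programmer working from SAP 10.7.2.5 would compute T − B.

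Baseline discharge may also be low. Recent respiratory symptoms and clinically active rhinitis are exclusions, and the baseline for positive participants precedes the positive result. That would make the residual small in grams. The share left would be the same, and T − B would then simply be the total under another name.

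Three stronger readings are tempting, and the documents do not support them:

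- **That the endpoints are compromised.** The protocol endpoints are the totals, which do not use the baseline.
- **That the comparison of arms is biased.** No test is attached to either endpoint. The baseline collection and the dosing start are both set before first IMP, and randomisation balances them in expectation across all randomised participants. Only chance imbalance goes largely uncorrected.
- **That a daily mean would cure unequal windows.** Starts on Day 2 and Day 5 cover different phases of illness, so their daily means are not fully equivalent.

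**Conclusion.** The point holds as a defect in a derived summary. As written, the change from baseline for mucus weight and tissue count mixes a total over about 7 to 10 collections with a one-day value. It keeps 86% to 90% of the usual-level contribution (88% to 91% if the dosing-day collection counts, k = 8 to 11) and shifts with dosing start.

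These shares rest only on a stable usual daily level. The gram values and simulation SDs are illustrative assumptions. The consequence is limited to an uninterpretable descriptive figure for two secondary endpoints, with almost no gain in precision from the baseline. The primary analysis and every tested endpoint are untouched. It should still be corrected, because the text, table list and shell cannot all be followed.

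**What to change.** In SAP 10.7.2.5:

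1. Keep both totals as the protocol-defined endpoints and report them without a change from baseline.
2. Define change like for like. Either take the mean 24-hour value (total divided by the number of collections) minus the 24-hour baseline, or take the change for each collection and then average or sum it, as SAP 10.7.2.4 does for symptoms. Averaging is preferable where windows differ, because a sum still grows with k.
3. State which collection opens the sum, so that the baseline collection cannot also be its first term.
4. Reconcile the section with the table titles in SAP 13.2, the shell in Section 14 and Listing 16.2.6.4.1, and record the added change from baseline in Section 11.

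No new data are needed. The cost is one extra derived row per endpoint and a shell edit. Two limits remain: the daily mean still spans different phases of illness for early and late starts, and a baseline from a single day carries that day's noise into the change.

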10.8. Pharmacokinetic Analysis

Summary of the pharmacokinetic (PK) data and endpoints will not be performed by S-cubed and will therefore not be a part of this SAP. Details of the PK Analysis will be found in the CPAP provided by VENN. Discussion of the PK parameter correlation can be found in Section 10.7.3.1..

10.9. Safety Analysis

All analyses of safety endpoints will be descriptive only. The safety population will be used for all safety presentations.

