- Peak symptoms diary card score: peak total clinical symptoms (TSS) as measured from 10 symptoms within the graded symptom scoring system collected 3 times daily starting from initial administration of IMP up to planned discharge from quarantine (Day 12, am).
- Peak daily symptom score: individual maximum daily sum of symptom score from initial administration of IMP up to planned discharge from quarantine (Day 12, am).
- Time (days) to symptom resolution as measured from 10 symptoms within the graded daily symptom scoring system starting at initial administration of IMP to time of returning to baseline score.
- Time (days) to symptom resolution as measured from 10 symptoms within the graded daily symptom scoring system starting at peak symptoms after initial administration of IMP to time of returning to baseline score.
- Time (days) to peak as measured from 10 symptoms within the graded daily symptom scoring system starting from initial administration of IMP to the time of peak daily symptom score.
- Total weight of mucus produced starting at initial administration of IMP up to planned discharge from quarantine (Day 12, am).
- Total number of tissues used by participants starting at initial administration of IMP up to planned discharge from quarantine (Day 12, am).

- Safety data including, but not limited to:
 - Occurrence of adverse events (AEs) from initial administration of IMP up to the Day 28 follow-up.
 - Occurrence of serious AEs (SAEs) from initial administration of IMP up to the Day 28 follow-up.
 - Occurrence of AEs related to the viral challenge from viral challenge (Day 0) up to the Day 28 follow-up.
 - Occurrence of SAEs related to the viral challenge from viral challenge (Day 0) up to the Day 28 follow-up.
 - Use of concomitant medications from viral challenge (Day 0) up to the Day 28 follow-up.
- Secondary endpoints related to PK include, but are not limited to:
 - Time to maximum plasma concentration (t_{max}), terminal half-life ($t_{1/2}$), maximum observed plasma concentration (C_{max}), area under the plasma concentration-time curve from time zero to the end of the dosing interval (AUC_{τ}), area under the plasma concentration-time curve over the last 24 hours dosing interval (AUC_{0-24h}) and area under the plasma concentration-time curve from time zero to infinity ($AUC_{0-\infty}$).

CCI [REDACTED]

[REDACTED]

[REDACTED]

[REDACTED]

■ CCI [REDACTED]
■ [REDACTED]
■ [REDACTED]
■ [REDACTED]
■ [REDACTED]

CCI

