9.6. Safety Population

The safety population will consist of all randomised participants who received challenge virus and at least 1 dose of IMP. Participants will be analysed according to the treatment they received.

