10.5. Prior and Concomitant Medications

Prior and concomitant medication terms will be coded using the World Health Organisation (WHO) Drug Dictionary Enhanced (WHO Drug Global, Version March 1 2022). A medication will be assigned as being prior to inoculation based on the start and stop dates of the medication and the date of challenge agent inoculation. If the medication stop date is before the inoculation date, the medication will be assigned as being prior to inoculation. A medication will be assigned as being prior to IMP or concomitant with IMP, based on the start and stop dates of the medication and the IMP. If the medication stop date is before the IMP start date and after the date of inoculation, the medication will be assigned as being prior to IMP. In all other situations, the medication will be assigned as being concomitant with IMP. If a participant has separate periods of taking specific medications, then that medication is only counted once within the specific period of observation (i.e., prior, or concomitant) where it is taken.

Note: Start and Stop times will not be used for determining if a medication is concomitant or not.

Concomitant medications up to the Day 28 visit will be summarised, using the Safety Population, by treatment group (and across all participants), Drug Class (L3) and preferred base name (01001). If Level 3 is missing for a medication then Level 2 will be used instead.

Prior medications will not be summarised but these will be listed.

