10.9.1. Adverse Events

All adverse events (AE) will be coded using MedDRA, Version 25.0.

An adverse event is defined as treatment emergent if the onset date is on or after the date of first dosing with IMP. Should any onset date for an adverse event be missing or only a partial date recorded (such that it cannot be determined if the event onset was prior to start of IMP or not) then it will be assumed that the event is treatment emergent, unless the adverse event stop date indicates otherwise.

Similarly, an AE is defined as challenge emergent if the onset date is on or after the date of inoculation. Should any onset date for an adverse event be missing or only a partial date recorded (such that it cannot be determined if the event onset was prior to inoculation or not) then it will be assumed that the event is challenge emergent, unless the adverse event stop date indicates otherwise.

An AE can be both challenge emergent and treatment emergent. Any AE with an onset date earlier than the inoculation date will be classified as a pre-treatment AE.

If a participant experiences more than one adverse event with the same preferred term, that preferred term will be counted only once. It will be assigned the greatest observed severity and the strongest relationship to IMP among those events for the tables in which those characteristics are summarised.

Pre-treatment AEs will be identified in a patient listing.

A summary of treatment-emergent AEs will be presented by treatment group showing the number of events, number of participants with events (also split by severity; mild, moderate, severe), number of participants with SAEs, number of participants with related events, number of participants with events

leading to early withdrawal from the study and the number of participants with events leading to early discontinuation of IMP.

Further summaries will present the treatment-emergent AEs by:

- Treatment group, SOC and PT.
- Treatment group, SOC, PT and severity.
- Treatment group, SOC, PT and relationship to IMP.

Further summaries will present the challenge-emergent AEs by:

- Treatment group, SOC, PT and relationship to challenge agent.

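### Challenge-virus safety is tabulated only in dosed participants, and two endpoints that start on Day 0 are not fully delivered for the period before the first dose

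*SAP*

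**What the plan says.** SAP 9.6 defines the set: "The safety population will consist of all randomised participants who received challenge virus and at least 1 dose of IMP". SAP 10.9 applies it throughout: "The safety population will be used for all safety presentations". The table of AEs related to the challenge agent (Table 14.3.1.5 in SAP 13.2) is assigned to it.

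Monitoring the safety of the challenge virus is an objective of its own (Protocol section 3, SAP 5.2). SAP 7.2 gives it three endpoints. The one for AEs reads "Occurrence of AEs related to the viral challenge from viral challenge (Day 0) up to the Day 28 follow-up". A second endpoint covers serious events over the same window. The third concerns treatment taken alongside and is worded as follows: "Use of concomitant medications from viral challenge (Day 0) up to the Day 28 follow-up".

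Under SAP 6.1, inoculation is on Day 0 and randomisation follows. First dosing is on the evening of Day 2 at the earliest, and on the evening of Day 5 if no qicPCR is positive.

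SAP 10.9.1 has two emergence rules. The first is "An adverse event is defined as treatment emergent if the onset date is on or after the date of first dosing with IMP". The second makes an AE challenge emergent from the date of inoculation, and those events are summarised by relationship to the challenge agent. Participants with SAEs are counted only in the treatment-emergent overview.

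SAP 10.5 classes medication stopped after inoculation and before the IMP start date as prior to IMP, and adds "Prior medications will not be summarised but these will be listed".

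**The concern.** A challenge study gives two exposures at different times. The virus comes first and the drug follows days later. A set that requires the drug is right for drug safety. For virus safety, the people at risk are all who were inoculated. Someone who leaves, is withdrawn or has dosing halted between the two exposures has been exposed to the virus, and an early virus-related event is one possible reason. That person would be missing from both numerator and denominator of the only challenge-agent AE table.

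Two further gaps concern participants who are dosed. The Day 0 SAE endpoint has no count that reaches back before the first dose. The Day 0 medication endpoint loses whatever was stopped before that dose. SAP section 11, which lists changes from the protocol, mentions neither.

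**Working it through.** The plan gives no figure to reproduce. The check follows each type of pre-dose record to the output where it would appear, and then gives a scale.

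**1. Challenge-related AE, participant inoculated but never dosed.** SAP 9.6 excludes the participant, and SAP 10.9 and Table 14.3.1.5 use that set. The event appears in Listing 16.2.7 only. The disposition shell (SAP 14) counts those who received the challenge agent separately from those randomised, and offers never having been dosed as a reason for withdrawal.

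**2. Challenge-related AE before first dose, participant later dosed.** It is challenge emergent under SAP 10.9.1 and is tabulated in Table 14.3.1.5. There is no gap in intent. However, that table reuses the shell of Table 14.3.1.4, which carries a footnote defining events from first IMP administration. The SAP supplies a replacement footnote on relationship but does not remove the other one.

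**3. Challenge-related SAE before the first-dose date, participant later dosed.** It enters Table 14.3.1.5 by preferred term, without being identified as serious. The only SAE count is in the overall treatment-emergent summary, where this event does not qualify. The Day 0 SAE endpoint therefore has no count for this period.

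**4. Medication.** Compare SAP 10.5 with the note under the Table 14.1.4 shell:
- Stopped after the inoculation date and before the IMP start date: prior to IMP, listed only.
- Stopped on the inoculation date: neither before nor after that date, so it falls into the residual class of SAP 10.5 and becomes concomitant with IMP. The Table 14.1.4 note requires a stop date not before the IMP date. Dosing cannot start before Day 2, so the note excludes it. The two rules disagree.
- Still in use at first dose: summarised, whenever it was started.

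**5. AE earlier on the first-dose date.** SAP 10.9.1 compares dates, so the event counts as treatment emergent. Onset time is collected (Protocol 10.3.6.1) and shown in Listing 16.2.7. SAP 10.1.1 already uses date and time to place Day 0 assessments before or after challenge.

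**6. Length of the pre-dose period.** No clock times are given. Assume inoculation between 08:00 and 18:00 and an evening dose at 20:00.
- Shortest: 2 + 20/24 − 18/24 = 2.08 days; 2.08/28 = 7.4% of the Day 0 to Day 28 window.
- Longest: 5 + 20/24 − 8/24 = 5.5 days; 5.5/28 = 19.6%.

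**7. Chance that someone is never dosed.** The documents give no rate *p*. For 80 inoculated, the expected number is 80*p* and P(at least one) = 1 − (1 − *p*)^80.
- *p* = 1%: 0.8 expected; 1 − 0.99^80 = 55%.
- *p* = 2%: 1.6 expected; 1 − 0.98^80 = 80%.
- *p* = 5%: 4.0 expected; 1 − 0.95^80 = 98%.

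**8. Effect on a reported rate (illustration).** Suppose 80 are dosed, one more is inoculated but not dosed, and that person has the only challenge-related SAE.
- Dosed participants only: 0/80, two-sided 95% upper limit 1 − 0.025^(1/80) = 4.5%.
- All inoculated: 1/81 = 1.2%, exact 95% interval 0.03% to 6.7%.

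**The case against.** The strongest reply is that little is lost. Every inoculated participant is meant to be dosed by the evening of Day 5, as an inpatient, and early withdrawal is strongly discouraged (Protocol 7.1). Those who are not dosed still appear in the disposition counts, and all collected data are listed (SAP 10.1.2). SAEs must be reported within 24 hours from the time of consent (Protocol 10.3.10). Safety analysis is descriptive only. All of this stands and limits the size of the point. It does not supply a summary of endpoints that the plan itself defines from Day 0.

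Some stronger readings are tempting, and the documents do not support them:
- A reader might infer that all events between inoculation and first dose are dropped or misassigned, so that 7% to 20% of the window goes unsummarised. The challenge-emergent rule in SAP 10.9.1 tabulates the challenge-related AEs of everyone later dosed.
- A reader might trace every gap to the safety set. The medication classes and the date-only rule are separate drafting choices.
- A reader might infer that medication stopped on Day 0 will be reported as concomitant with IMP. The Table 14.1.4 note says otherwise, so what is established is a conflict between two rules.
- A reader might conclude that the date-only rule moves many RSV symptoms into the treatment-emergent counts. Typical diary-card symptoms are not AEs unless clinically significant (Protocol 10.3.1 and 10.3.6.2). The rule affects one calendar day, applies to both blinded arms and leans towards inclusion. A figure of up to 20 hours would rest on an assumed 20:00 dose.
- The never-dosed category need not describe people who left before randomisation, because percentages in that shell are based on randomised participants. It shows that inoculated participants without a dose are possible, and says nothing about how many.

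**Conclusion.** The point holds in a limited form. Anyone inoculated but never dosed is outside every safety table, despite an objective that starts at inoculation. Challenge-related SAEs before the first-dose date have no count. The Day 0 medication endpoint is not delivered as defined. The conflict over medication stopped on the inoculation date and the date-only emergence rule are smaller, separate matters.

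The practical size depends on how many participants are never dosed, which the documents do not state. It may be zero, and the 55% to 98% above follows only from the assumed 1% to 5%. The medication and SAE gaps do not depend on that number, because they also affect dosed participants. No efficacy result or hypothesis test is touched. The change is worth making before unblinding because it alters what stated endpoints report.

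**What to change.** Protocol 9.3 allows further analysis sets to be defined in the SAP, so a SAP revision is enough.

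1. Define an all-inoculated set, with a column for participants inoculated but not dosed.
2. Use it for Table 14.3.1.5, for a new count of participants with challenge-related SAEs from Day 0, and for medication use from Day 0, including medication stopped before first dose.
3. Reconcile SAP 10.5 with the Table 14.1.4 note for medication stopped on the inoculation date.
4. State that the treatment-emergent footnote of the Table 14.3.1.4 shell does not apply to Table 14.3.1.5.
5. Assign treatment emergence by date and time where a time is recorded, keeping the present conservative rule where it is missing.
6. Keep the Safety population for IMP safety, and record the changes in SAP section 11.

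The cost is one set, one column, one SAE count and one medication summary. No new data are needed: onset times are already collected, and the medication listing already flags the period between inoculation and IMP. The added column may turn out empty.
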